In order to investigate this hypothesis, we want to perform the HORUZ study. We are interested in the fluid status, BP and thoracic BIS signal of patients with CKD 3 - 5, not on dialysis. We aim to provide more evidence to further support the frequent use of BIS in diagnostic guidelines of patients with CKD.

OBJECTIVES

The primary objective of the HORUZ study is to associate fluid status with kidney function decline in patients with CKD stage 3 (CKD-EPI eGFR 60-30ml/min), 4 (30-15ml/min) and 5 (< 15 ml/min) and compare them to an age- and sex- matched healthy control group. Primary outcome is the mean eGFR decline which will be compared between the FO-group and the non-FO-group.

The secondary objective is to identify the clinical factors associated with FO during a longitudinal follow up. Secondary outcomes of interest are the central volume status (measured by echocardiography and thoracic BIS in combination with photoplethysmography), the cardiac systolic and diastolic function, CV events, hospitalizations, inflammatory- and nutrition status, and quality of life, between CKD stages 3, 4 and 5 and compare them to an age- and sex- matched healthy control group.

STUDY DESIGN

The HORUZ study is a non-randomized trial with intervention of regular BIS- and BP measurements, blood- and urine sampling. Prevalent patients with CKD stages 3, 4 and 5 and an age- and sex- matched healthy control group will be included. Inclusion period will last 18 months and CKD-patients will be followed up for 12 months.

STUDY POPULATION

1. Population

206 patients with CKD stages 3-5 will be included from the outpatient clinic of Ziekenhuis Zuid-Oost Limburg in Genk (Belgium).

A healthy control group for the cross-sectional part will be recruited through visitors and/or personnel of Ziekenhuis Oost-Limburg in Genk (Belgium).

2. Inclusion criteria

In order to be eligible to participate in this study, a subject must meet the following criteria:

- Prevalent non-dialysis patients with eGFR < 60 ml/min (for CKD subjects)
- Age > 18 years
- Signed informed consent

3. Exclusion criteria

A subject who meets any of the following criteria will be excluded from participation in this study:

- Acute kidney injury
- eGFR < 20ml/min directly post-nephrectomy
- Clinical conditions affecting BIS measurements: limb amputation, impaired skin integrity, brain stimulator, pacemaker with low threshold or unipolar pacemaker.

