- Clinical conditions affecting body composition: liver cirrhosis, active infectious disease or any acute CV event (defined as cerebrovascular event, myocard infarction, decompensatio cordis) during the 3 months before screening for inclusion
- Pregnancy

- Not able to sign informed consent

4. Sample size calculation

The primary outcome parameter is the mean eGFR decline which will be compared between the FOgroup and the non-FO-group. We hypothesize that the mean difference between eGFR between these two groups will be 2 μ mol/ml/year. Because the study of Levin et al. does not report a SD, we take the SD of the MDRD study¹: 4.7 μ mol/ml/year^{1,42,43}. In order to show an alpha of 0.05 and a power of 0.8, at least 86 patients would be needed per group. In order to correct for drop-outs, at least 103 patients per group have to be included.

METHODS

1. Study parameters/endpoints

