1.1 Demographic and clinical data

The prevalent CKD stage 3 – 5 population will be screened by the researcher. After verification of the in- and exclusion criteria, eligible patients will be invited to participate the HORUZ study, with approval of their treating nephrologist. After signing the informed consent, data at baseline and during followup visits will be collected on paper clinical report forms (Table 1). Hypertension is defined as an office BP \geq 140/90 mmHg or home BP \geq 130/80 mmHg, or current medication for hypertension.¹ Diabetes mellitus will be assumed to be present in patients who report use of insulin and/or oral hypoglycemic agents. CV diseases include coronary artery disease, as documented by coronary angiography or a history of myocardial infarction, congestive heart failure, cerebrovascular accident, or known peripheral vascular disease. Fluid assessments, including BIS measurements, will be recorded on the HORUZ registration form (Appendix).

The healthy controls included for the cross-sectional analysis will only be followed according to visit 0 and 1.

| | Baseline Visit 0 | Month 1 Visit 1 | Month 3 Visit 2 | Month 6 Visit 3 | Month 9 Visit 4 | Month 12/ end of study Visit 5 |
|--|---------------------|--------------------|--------------------|--------------------|--------------------|-----------------------------------|
| Consent | х | | | | | |
| Demographics: Age (y) Gender Height (cm) Smoking status Etiology CKD Hypertension Diabetes CV disease Tx list | x | | | | | |
| eGFR _{creat} | x | x | x | x | x | x |
| CrUrCl | | x | x | x | x | x |
| 24h urine | | x | x | x | x | x |

Table 1 Schedule of the main data to collect in CKD subjects.

| BP | x | | x | x | x | x |
|-----------------|---|---|---|---|---|---|
| ECG | x | | x | x | x | x |
| Echo cor | | x | | | | x |
| CV events | | x | x | x | x | x |
| Hospitalization | | x | x | x | x | x |
| Medication | x | | x | x | x | x |
| Whole body BIS | x | | x | x | x | x |
| Thoracic BIS | x | | x | x | x | x |
| SF36 | x | | | | | x |
| Adverse event | | x | x | x | x | x |

Abbreviations: BIS, bioimpedance spectroscopy; BP, blood pressure; CKD, chronic kidney failure; Creat, creatinine; CrUrCl, mixed creatinine

and urea clearance; CV, cardiovascular; ECG, electrocardiography; M, month; SF36, short form 36 questionnaire; Tx, transplantation.

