1.3 Secondary endpoints

The secondary objective is to identify the clinical factors associated with FO during a longitudinal follow up. Secondary outcomes of interest are the central volume status (measured by echocardiography and thoracic BIS in combination with photoplethysmography), BP, the cardiac systolic and diastolic function, CV events, hospitalizations, inflammatory- and nutrition status, and quality of life, between CKD stages 3, 4 and 5.

- 1. *Cardiac function:* Electrocardiography and echocardiography (see point 3.3) will be scheduled at baseline, and at 12 months or at end of study visit.
- Thoracic BIS values: a wearable device from Imec Eindhoven will be used to measure thoracic
 BIS values in combination with photoplethysmography and cardiopulmonary index.
- 3. *Blood pressure:* patients will be asked to take BP measurements at home three times a week twice daily with an automatic BP monitor. Mean arterial pressure corrected for heart

frequency will be calculated. BP measurements can be transmitted to the researcher by use of the local Dharma platform.

- 4. *CV events:* CV events defined as hospitalization for coronary disease, heart failure, stroke or peripheral artery disease will be recorded during follow-up.
- 5. *Hospitalization rate and indication:* hospitalization rate and indication will be listed.
- 6. *Inflammatory- and nutrition status:* CRP, ferritin and albumin will be determined every visit (Table 2). Fat tissue mass and lean tissue mass will be analyzed by BIS measurements.
- 7. *Quality of Life assessment:* SF36 questionnaire will be filled in at baseline and end of study visit.

| Table 2 Overview of | f parameters evaluatir | g kidney function, r | enal metabolism a | and inflammation in HORUZ study. |
|---------------------|------------------------|----------------------|-------------------|----------------------------------|

| Assay | Material | Standard care | Frequency |
|-------------------------|--------------|---------------|-------------------|
| Residual renal function | | | |
| Urea | Plasma/serum | yes | Every study visit |
| Creatinine | | | |
| Metabolism and electrol | ytes | | |
| Hemoglobin | Plasma/serum | yes | Every study visit |
| Sodium | | | |
| Potassium | | | |
| Bicarbonate | | | |
| Phosphate | | | |
| Calcium | | | |
| NT-proBNP | | No | Every study visit |
| Inflammation | | | |
| C-reactive protein | Plasma/serum | yes | Every study visit |
| Leucocytes | | | |
| Albumin | | | |

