2.3 Suspected unexpected serious adverse reactions (SUSAR)

Not applicable.

3. Follow-up of adverse events

AE according to the study are considered very unlikely, due to the fact that only non-invasive methods are used. All AEs will be followed until a stable situation has been reached and treated to standard procedures.

4. Data Safety Monitoring Board (DSMB)

Not applicable.

STATISTICAL ANALYSIS

A table with baseline characteristics of all subjects will be provided. Baseline characteristics of the population will be expressed as the mean \pm standard deviation if normally distributed, or as the median [25th – 75th percentile] as not normally distributed, for continuous and dichotomous data, and as the frequency (%) for categorical data. Measurements of drop-outs will be included until the moment of withdrawal from the study. Normality in distribution will be tested by the Shapiro-Wilk statistic. Repeated measurements ANOVA techniques will be used for analysis. Pearson's Chi-squared test will be used to assess whether there is any distinction between subgroups in rate of kidney function decline. In case the analysis of the baseline characteristics showed any clinically relevant imbalance, we will also perform a multivariable logistic regression analysis in order to correct for this imbalance. Differences in LVH will be corrected for systolic BP and haemoglobin, as these are predictors of LVH in predialysis population.¹⁵ Depending on the level of measurement a Chi-squared test or a T-test will be used to assess differences in secondary study parameters, and logistic and linear regression for baseline-corrected estimates. Tests will be considered significant if p-values are ≤ 0.05 .

ETHICAL CONSIDERATIONS

1. Regulation statement

The study will be conducted according to the principles of the Declaration of Helsinki (Fortaleza, Brasil, 2013).

2. Recruitment and consent

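### The T-test named for continuous secondary outcomes does not fit a comparison across three CKD stages and healthy controls, and no multi-group test is assigned to it

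*Combined protocol and SAP*

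**What the plan says.** **Groups.** The Summary and the Objectives set the comparison of secondary outcomes as "between CKD stages 3, 4 and 5 and compare them to an age- and sex- matched healthy control group", which is four groups. Section 1.3 (Secondary endpoints) ends the same list with "inflammatory- and nutrition status, and quality of life, between CKD stages 3, 4 and 5" and does not mention controls, which leaves three groups.

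**Control data.** Section 1.1 states: "The healthy controls included for the cross-sectional analysis will only be followed according to visit 0 and 1".

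**Tests.** The Statistical analysis section assigns tests to these outcomes in one sentence. It says that "a Chi-squared test or a T-test will be used to assess differences in secondary study parameters", the choice following the type of variable. The rest of that sentence brings in modelling: "and logistic and linear regression for baseline-corrected estimates". Earlier in the same paragraph stands "Repeated measurements ANOVA techniques will be used for analysis", with no outcome and no grouping factor named. Differences in LVH are to be corrected for systolic BP and haemoglobin.

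**Threshold.** "Tests will be considered significant if p-values are ≤ 0.05". The section names no overall test across groups, no post-hoc procedure and no multiplicity rule for the secondary outcomes.

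**Secondary objective.** The Summary, the Objectives and section 1.3 all give the secondary objective as finding clinical factors associated with FO. The stage and control contrasts are listed after it, as outcomes of interest.

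**The concern.** Many of the listed outcomes are continuous or usually analysed as such: LVEF, LV mass index, thoracic BIS values, BP, CRP, ferritin, albumin, lean and fat tissue mass, SF36. For these, the only unadjusted test named compares two groups, while the stated comparison has three or four. Someone applying the plan must choose between testing pairs, pooling stages, or borrowing another method from the same paragraph, and could make that choice after seeing the data.

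Two things are at stake. If pairs are tested one by one at 0.05, the error rate per outcome rises well above 5%. A T-test also ignores the order of the stages and makes no allowance for age or sex, although a trend across stages is the natural reading of the question.

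**Working it through.** **1. The plan's own figure.** The documents give no error rate for the secondary comparisons. Their one calculation is for the primary comparison of FO with non-FO: "In order to show an alpha of 0.05 and a power of 0.8, at least 86 patients would be needed per group". With a difference of 2, an SD of 4.7 and a two-sided 0.05:

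n = 2 × [4.7 × (1.960 + 0.842) / 2]² = 86.7 per group.

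The stated 86 is reproduced to within rounding; power at 86 is 79.7%. It is a two-group calculation at 0.05 and does not bear on the stage comparison. It leads to 103 per group after dropout, so 206 CKD patients in all.

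**2. Number of pairs.** For g groups there are g(g − 1)/2 pairs.
- Three stages: 3 × 2 / 2 = 3 pairs.
- Three stages plus controls: 4 × 3 / 2 = 6 pairs.

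**3. Error rate if every pair were tested at 0.05 and all means were equal.** If the tests were independent, the chance of at least one false positive would be 1 − 0.95^m:
- m = 3: 1 − 0.95³ = 14.3%.
- m = 6: 1 − 0.95⁶ = 26.5%.

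Pairs that share a group are correlated, so the true rates are lower. They were simulated with normal data, equal means and variances, pooled T-tests and 100,000 runs per row. The split by stage and the number of controls are not in the documents. The sizes below are therefore assumptions; the CKD groups sum to 206.

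| Assumed sizes (stage 3 / 4 / 5 / controls) | All pairs at 0.05 | Bonferroni | One overall F test |
|---|---|---|---|
| 69 / 69 / 68 / none | 12.0% | 4.4% | 4.9% |
| 120 / 60 / 26 / none | 11.9% | 4.2% | 4.9% |
| 69 / 69 / 68 / 69 | 20.4% | 4.2% | 5.0% |
| 69 / 69 / 68 / 30 | 20.3% | 4.1% | 5.0% |
| 120 / 60 / 26 / 50 | 20.0% | 4.1% | 5.0% |
| 69 / 69 / 68 / 206 | 19.7% | 4.0% | 4.9% |

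Bonferroni uses 0.05/3 = 0.0167 for three pairs and 0.05/6 = 0.0083 for six. The simulation error is about √(0.2 × 0.8 / 100,000) = 0.13 percentage points or less. The results hardly depend on the assumed split.

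**4. Which named method could carry the comparison?**
- *Chi-squared test:* takes three or four groups in one overall test, so the inflation in step 3 does not arise for categorical outcomes.
- *T-test:* two groups only.
- *Linear and logistic regression:* can take a multi-level group factor. The plan offers them for baseline-corrected estimates and gives no group coding, no covariate list and no overall test.
- *Repeated-measures ANOVA:* can take a group factor, but is tied to no outcome. For several control contrasts nothing is repeated. If controls follow the visit 0 and visit 1 columns of Table 1, whole-body BIS, thoracic BIS and SF36 fall at visit 0 only, and echocardiography at visit 1 only.

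**5. How many groups for which outcome.** Controls stop after visit 1. Four groups are possible only for cross-sectional outcomes measured at visits 0 and 1. Outcomes at 12 months or over follow-up have three groups.

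**The case against.** The strongest reply is that the plan never says pairwise T-tests will be run between stages. The T-test may be meant for FO versus non-FO, which is a two-group comparison and matches the stated secondary objective. The Chi-squared test covers categorical outcomes with any number of groups, and the sentence that names the T-test goes on to name linear and logistic regression, which can handle a stage factor. The 12% and 20% also assume equal means in every group. For several outcomes that is unlikely: the Introduction itself links kidney function decline to LV mass index, BP and CV events. Finally, these are secondary outcomes in a non-randomized cohort, and how strictly to adjust them is partly a matter of judgement.

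Most of this stands, and it limits the point. Three stronger readings are tempting, and the documents do not support them:
- *That the plan commits to an error rate of 12% or 20%.* These figures hold only if all pairs are tested and all means are equal.
- *That control contrasts are confounded by age because matching is to the whole cohort.* The documents say only that controls are matched on age and sex. They give no matching unit, ratio or number of controls, and do not exclude matching within stage.
- *That the stage contrast is the secondary objective.* That objective concerns factors associated with FO.

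The mismatch remains. If the T-test is for FO versus non-FO, the stage and control comparisons of continuous outcomes have no unadjusted test assigned. If it is for the stages, it does not fit them. Either way the plan needs a correction.

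**Conclusion.** The point holds in a limited form: for continuous secondary outcomes, the named T-test does not fit a three- or four-group comparison, and the methods that would fit are not linked to it. The possible inflation is about 12% (three stages) or 20% (four groups) per outcome, against 5% for one overall test, on the condition of all-pairs testing at 0.05 under equal means. Whether three or four groups apply is itself unsettled between the Objectives and section 1.3. Multiplicity across the seven numbered items in section 1.3 is a separate matter, not counted in these figures. This should be corrected, but it does not touch the primary endpoint or the sample size.

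**What to change.** In the Statistical analysis section:
- Keep the T-test for two-group comparisons such as FO versus non-FO, and the Chi-squared test for categorical outcomes.
- For stage and control comparisons of continuous outcomes, fit one linear model per outcome with a group factor: four levels for cross-sectional outcomes measured in controls at visits 0 and 1, three levels for 12-month and follow-up outcomes.
- Include age and sex as covariates, because the documents do not say that matching is within stage.
- Report one overall test and a linear trend over stages 3-4-5.
- Give any pairwise contrasts with Tukey or Holm adjustment. Unadjusted contrasts after a significant overall test are not enough with four groups: if controls differ from CKD patients while the stages are equal, the overall test will usually be significant and the three stage pairs still carry about 12%.
- State in section 1.3 which outcomes are compared with controls, so that it agrees with the Objectives.

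The cost is a few sentences and slightly wider pairwise intervals. No new data are needed.

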APPENDIX: HORUZ REGISTRATION FORM

| Studynumber: HZOL | | | | | | | | | | | |
|---|------------|--|------------------------|----------|--|--|------------|------|---|--|--|
| Age yGenderM / FHeight cmSmoking statusno / yes / smoking cessation date:Etiology CKDHypertensionno / yesDiabetesno / yesCV diseaseno / yes:Tx listno / yes | | | | | | | | | | | |
| Visit number date | complains* | | office BP ⁵ | oedeem** | BIS thoracaal BIS whole body TBW / ECW / ICW OH / LTM / FTM | Cardiac function ECG Echo cor | Medication | SF36 | homeBP [¥] morning evening | Kidney function eGFR _{creat} CrUrCl 24h urine | CV event Hospitalisation AE/ SAE |
| 0 | | | | | / / | | | | | | |
| 1 | | | | | | Date echo cor: | | | | | |
| 2 | | | | | / / | | | | | | |
| 3 | | | | | | | | | | | ··· ··· |

| 4 | | | / / | | | | |
|-------|------|------|-----|-----------|------|------|--|
| | | | / / | | | | |
| | | | | | | | |
| 5/End | | | / / | | | | |
| | | | | Date | | | |
| | | | | echo cor: | | | |
| | | | | | | | |
| | | | | | | | |

Abbreviations: AE adverse event, BIS bioimpedance spectroscopy, BP blood pressure, ECW extracellular water, ICW intracellular water, FTM fat tissue mass, LTM lean tissue mass, OH overhydratie, TBW total body water, SAE severe adverse event

§ office BP: BP measured during visit

¥ home BP: mean of home measurements

*complains: dyspnoe 1, orthopnoe 2, druk op de borst 3, palpitaties 4, pijnlijke gezwollen voeten 5, spierkrampen 6, duizelig 7, dorst 8, obstipatie 9, anders 10

**perifeer oedeem: geen 1, matig 2, veel 3

AE: any undesirable experience occurring to a subject during the clinical trial, whether or not considered related to the investigational treatment.

SAE: results in death; or requires hospitalization or prolongation of existing inpatients' hospitalization; or results in persistent or significant disability or incapacity; or is a new event of the trial

likely to affect the safety of the subject, such as an unexpected outcome of an adverse reaction
